## **B. Description of Population to be Enrolled**

Inclusion Criteria. 1) Member of the Naval Surface or Aviation Forces; 2) Age: 18-55 years at the time of enrollment; 3) History of at least one deployment with return to permanent station within the past 36 months, or stationed outside the Continental United States with permanent change of station (PCS) to the Continental United States within the past 36 months, or any PCS move within the past 36 months or on initial command duty assignment; 4) Ability to provide verbal and electronic informed consents; 5) Ownership of smartphone; and 6) Willingness to use smartphone and personal data plan to participate.

Exclusion Criteria. 1) Having an iPhone (until the Cogito Corporation releases the iOS version of the Cogito Companion app).

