## **I. Hypotheses and Specific Aims**

**Aim 1.** Evaluate the efficacy of the Cogito Companion as an upstream suicide prevention intervention.

**Hypothesis 1.1.** Participants allocated to the Cogito Companion will report significantly fewer episodes of distress and less distress over the course of the study (Outcome Questionnaire-45; OQ-45) compared to those allocated to the Active Control group.

**Hypothesis 1.2.** Among those with episodes of clinically meaningful distress, those allocated to the Cogito Companion will more rapidly engage in treatment (medical record review and Client Services Receipt Inventory-EU-Revised; CSRI-EU-R) to address such symptoms versus those allocated to the Active Control group.

**Hypothesis 1.3.** Participants allocated to the Cogito Companion will report significantly fewer episodes of and less severe depressive (Patient Health Questionnaire-9; PHQ-9) and post-traumatic symptoms (Post Traumatic Stress Disorder Checklist-5; PCL-5), and suicide-related thoughts (Beck Scale for Suicide Ideation; BSS, Columbia-Suicide Severity Rating Scale Screener; C-SSRS Screener), as well as overall increased perceived physical/psychological health functioning (Rand 36-Item Health Survey; SF-36) over the course of the study compared to those allocated to the Active Control condition.

**Aim 2.** Evaluate the acceptability and feasibility of the Cogito Companion among military personnel (Sailors).

**Aim 2.1.** Acceptability of Cogito Companion will evaluate based on participant satisfaction (CSQ), participant engagement in application-related activities (e.g., leaving voice recordings), and time spent on the application. Acceptability refers to the suitability of an intervention from the perspectives of the participants.

**Aim 2.2.** Feasibility of Cogito Companion will be evaluated based on participant retention and accrual, and number and type (minor, moderate, severe) of technical challenges noted during implementation. Feasibility refers to the ease of implementation.

**Exploratory Aim.** Identify patterns of distress, depressive symptoms, post-traumatic symptoms, suicide-related thoughts, and perceived physical and psychological health functioning over the course of the study among the entire sample, as well as within the Cogito Companion and Active Control groups.

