Sailors will be provided with written and/or electronic consent materials. That is, Sailors will be provided with a written copy and/or an electronic copy(ies) of the consent materials. Consent will be obtained via MyCAP/REDCap. This will be facilitated and observed by the team members. During this process, Sailors will be asked to confirm that they have read consent materials and received a written and/or electronic version of consent materials. During the study visit, members of the research team will also explain monitoring processes, and outreach procedures. Such procedures will be initiated in the event that the study team receives technical or clinical data suggesting that such a contact is warranted (more information to be provided below). Participants will be asked to provide the study team with multiple phone numbers via MyCAP/REDCap or in written format for personal (e.g., spouse, friend) and/or provider contact in case the participant cannot be reached during a clinical monitoring outreach call (see below for clinical monitoring procedures).

Randomization will be stratified by gender, force (Surface versus Aviation), and smartphone type (i.e., Android, iPhone [once the iOS version is released]). Initially, only those with Android platform smartphones will be recruited. Once either application is assigned and/or downloaded, a member of the study team will provide the Sailor with the information to login (e.g., tokens). Participants will be provided with study team contact information, for any technical assistance while using the assigned modality, as well as information regarding monthly reimbursement for cell phone data usage (\$30 per month). They will all be provided with Military/Veterans Crisis Line Contact information, and may be provided with additional resources (e.g., local resources). All payments may be made via a MasterCard debit type card called a "ClinCard" that is provided by Greenphire. Funds are usually available via this card within 24 hours following the scheduled payment date (possible exceptions are weekends or holidays).

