**Authorization.** All required elements of informed consent will be provided on MyCAP/REDCap, including information regarding the purpose of the study, what to expect if participating, possible risks and discomforts, who is paying for the study, the voluntary nature of participating, whom to contact with questions, information regarding the privacy of participants' information, and exceptions to confidentiality. We will request a Waiver of Documentation of Consent and a HIPAA Waiver to facilitate conducting this study.

**Study Design.** Randomized Controlled Trial (RCT), with up to 1,418 individuals being allocated to Experimental (Cogito Companion) or Active Control (MyCAP) based on stratified randomization tables. Randomization will be stratified by gender, force (Surface, Aviation), and smartphone model (Android, I-Phone [once the iOS version is released]), as Cogito algorithms differ based on smartphone platforms. Data is also being collected (feasibility/acceptability) to inform future implementation.

**Study Procedures.** Upon confirming interest in participating in the study, a member of the research team will obtain verbal informed consent and confirm eligibility. Electronic consent will be provided via MyCAP/REDCap. Baseline measures will be administered via MyCAP/REDCap. Military personnel will then be randomized to the Cogito Companion group (Experimental) or the Active Control (MyCAP) group.

Biweekly (every other week) post-consent, study measures will be pushed to participants via the mobile apps (Cogito Companion, MyCAP). Post-completion of measures at the end of the study period (Follow-up Survey), participants will be provided with a link (MyCAP/REDCap). See Figure 1 for an outline of study procedures, and Table 1 for proposed measures and administration schedule.

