**Figure 2.**  
**Participant View**

*Random Allocation and Concealment.* Randomization to the Experimental or Active Control arms will be stratified by gender, force, and smartphone model. The block randomization schemes, using random block sizes of 2, 4, and 6, will be produced by [name] using Statistical Analysis System (SAS) PROC PLAN with a specified seed, prior to any recruitment. To ensure concealed allocation, participants will be designated by an identification number.

*Treatment Arms.* Experimental. Those allocated to Experimental arm will have access to the Cogito Companion for a three-month period post-

consent. Passive data collection will also occur during this period. As a secure, privacy-compliant mobile app, the Cogito Companion facilitates the non-invasive collection, transfer, integration, analysis, and reporting of objective behavioral indicators (Figure 2). The Cogito mobile sensing platform passively gathers behavioral information through an individual's normal smartphone usage. Measurements of location, call, and text patterns are recorded. These raw

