**Analysis Plan.** All analyses will assume a two-sided test of hypothesis, a significance level of 0.05 (unless otherwise indicated) and will be run in SAS v9.4 or higher, or R v3.3 or higher. To check randomization, demographic and clinical characteristics will be compared between groups using t-tests, chi-square tests or nonparametric tests, as appropriate. If any variable is found to be significantly different between the groups and is also plausibly associated with an outcome, it will be considered as potential confounders in the models described below.

**Aim 1.** To address the hypothesis regarding episodes of distress first using Poisson regression will be used to model the number (response rate) of episodes of distress as a function of group (0=Active Control, 1=Cogito), any potential confounders, and an offset of log (time) to account for varying lengths of follow-up. If the deviance is estimated to be  $> 1.5$ , Negative Binomial regression will be used instead, incorporating the same variables. The parameter estimate associated with the group variable will be exponentiated, providing an estimate of the ratio of response rates between the groups and will be reported with a 97.5% confidence interval (CI). To address the hypothesis regarding distress over the course of the study, a linear mixed-effects model will be employed with longitudinal OQ-45 scores as the dependent variable and group, potential confounders, and an interaction between group and time (using either natural cubic B-spline transformations on time or polynomial transformations on time) as independent variables. These transformations will also be applied to the random time effects so that individual trajectories can be calculated. Akaike's Information Criterion will be used to determine which model provides the best fit (both between the B-spline/polynomial models and within them). Once a final model is determined, the difference in AUC will be calculated and between groups and compared to the clinically meaningful AUC difference of 84 using a one-sided test. Here the null hypothesis is that  $AUC_{AC} - AUC_{Cogito} \geq 84$ , and the alternative hypothesis is that  $AUC_{AC} - AUC_{Cogito} < 84$ . The estimated difference will be reported with the one-sided 97.5% CI. For hypothesis 1.2, a Kaplan-Meier estimate will be used to compare the median time to treatment engagement

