between the groups and each median will be reported with 95% CIs. Treatment engagement is operationalized as a visit with any medical or mental health provider in which a mental health related ICD code is identified. and will be determined by medical record review. Additionally, the total number of mental health visits calculated from the CSRI-EU-R will be modeled using a Poisson or Negative Binomial regression model to estimate the difference in number of visits between the groups over the course of the study. The model will be set up similarly to the OQ-45 model. Hypothesis 1.3 is similar to hypothesis 1.1 such that we wish to look at episodes of depressive symptoms (PHQ-9), post-traumatic symptoms (PCL-5) and suicide-related thoughts (BSS) as well as severity of each over the course of the study. We also wish to look at perceived physical and psychological health functioning (RAND SF-36) over the course of the study. The methods employed to address hypothesis 1.1 will be utilized to estimate the difference in number of episodes of each outcome (excluding the SF-36) as well as the difference in AUC for each outcome. Zero-inflated negative binomial regression will be considered for the BSS if a large proportion of the participants do not exhibit suicidal thoughts and transformations will be considered for the AUC BSS analysis, given that it is likely to be highly skewed. Cutoffs for episodes of depressive/post traumatic symptoms, and suicidal thoughts are  $\geq 10$  (PHQ-9),  $\geq 33$  (PCL-5), and  $\geq 2$  (BSS), respectively.

***Aim 2.*** We will assess the proportion of participants who find the Cogito Companion acceptable, defined as  $\geq 70\%$  of participants scoring  $\geq 24$  on the CSQ. The proportion of Cogito Companion participants with a CSQ score of  $\geq 24$  will be calculated with a 95% CI. Additionally, the proportion of participants engaging in activities will be reported with a 95% CI as well as the median (range) amount of time spent on the application. Feasibility will be measured by the proportion of Cogito Companion participants who complete treatment and reasons for termination will be examined.

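### Randomization is stratified by gender, force and phone type, but no planned model contains these factors and no result is planned by platform

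*Protocol*

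**What the plan says.** Protocol IV.B excludes anyone "Having an iPhone (until the Cogito Corporation releases the iOS version of the Cogito Companion app". Section IV.C confirms the sequence: "Initially, only those with Android platform smartphones will be recruited".

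Section IV.C (Random Allocation and Concealment) states: "Randomization to the Experimental or Active Control arms will be stratified by gender, force, and smartphone model", "using random block sizes of 2, 4, and 6". The Study Design paragraph gives the reason for including the phone: "as Cogito algorithms differ based on smartphone platforms".

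Section IV.F, reprinted in the SAP, sets out the models. The episode model has group, potential confounders and a log-time offset. The OQ-45 mixed model has group, potential confounders and group by time. Hypothesis 1.3 reuses both. Hypothesis 1.2 is a Kaplan-Meier comparison. Acceptability, engagement and completion are simple summaries of the Cogito arm, for example "Feasibility will be measured by the proportion of Cogito Companion participants who complete treatment". The one route by which a covariate can be considered is: "If any variable is found to be significantly different between the groups and is also plausibly associated with an outcome".

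The SAP's revised Aim 1 compares time to first characterization of risk, counted from the availability of model scores, and names no model or covariates. The SAP also says that the team kept to the protocol's power analysis and analysis plan after the aims changed.

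**The concern.** A trial that balances its arms on three factors would normally carry those factors into its models. Otherwise the variation they explain stays in the error term, although randomization has already removed it from the comparison of arms, and the reported precision is worse than the design delivers. Here the covariate rule looks as if it might fill the gap, but it selects on baseline imbalance, which the stratification suppresses.

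Phone type has a second role. The sponsor gives algorithm differences as the reason for stratifying on it, and model scores drive both outreach in the Cogito arm and the clock for revised Hypothesis 1.1. If iPhone users enter, the Cogito result averages over two algorithm versions, and nothing in the plan shows whether they perform alike. Aim 2 describes the Cogito arm alone, so there is no control group to help interpret a mixed figure.

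**Working it through.** **1. The plan's own power figure.** Inputs from Protocol IV.F: N = 750 completers, rate ratio (RR) 0.85, two-sided 0.025, control mean m. Formula: power = Φ{[√(N·m)·|ln RR| − z·√V0]/√V1}, with V0 = 4, V1 = 2 + 2/0.85 = 4.353 and z = 2.241. At m = 3.5: √2625 × 0.1625 = 8.327; less 2.241 × 2 = 4.483 leaves 3.844; divided by 2.086 this is 1.842, so power is 96.7%. At m = 3, 2.5, 2 and 1.5 it is 93.9%, 89.0%, 80.7% and 67.9%. The plan states 97%, 94%, 89%, 81% and 68%. All five reproduce, and no term depends on strata or phone type, so adding the factors changes no stated sample size.

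**2. Can the baseline rule bring the factors in?** A block of 6 left incomplete can leave a stratum at most 3 apart. With both platforms open there are 2 × 2 × 2 = 8 strata, 4 per phone level, so the largest imbalance at one phone level is D = 4 × 3 = 12 (with the opposite imbalance at the other level). For equal arms, χ² = D²/[N·p(1 − p)], where N = 950 randomized and p is the iPhone share. The documents do not give p, so it is varied.

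| Assumed iPhone share | χ² | p-value |
|---|---|---|
| 50% | 144/237.5 = 0.61 | 0.44 |
| 30% | 144/199.5 = 0.72 | 0.40 |
| 20% | 144/152 = 0.95 | 0.33 |
| 10% | 144/85.5 = 1.68 | 0.19 |
| 5% (48 of 950) | 3.16 | 0.075 |
| 4% (38 of 950) | 3.95 | 0.047 |

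This is the extreme case: every stratum must end at its maximum, all in the adverse direction. The same bound applies to gender and force. While only Android is open there are 4 strata, 2 per level, so D is at most 6 and χ² is a quarter of these values.

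The bound depends on N. The extreme case crosses 0.05 when N·p(1 − p) < 144/3.841 = 37.5, which at an even split means fewer than 150 randomized. It covers everyone randomized, not subsets such as participants with distress.

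**3. Effect on precision.** In a linear model, adjusting for baseline factors that explain a share R² of the between-person variation multiplies the standard error by about √(1 − R²). In a negative binomial model the omitted factors appear as extra dispersion. The documents give no R² for gender, force or phone type, so the loss cannot be sized. It is zero if the factors do not predict outcome.

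**4. If iPhone users are enrolled.** Illustration with assumed inputs: m = 3.5, RR 0.85 on Android, RR 1.00 on iOS, iPhone share s. The pooled RR is 0.85(1 − s) + s, and pooled power uses the formula in step 1.

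| s | Pooled RR | Pooled power | Interaction power (5%) |
|---|---|---|---|
| 25% | 0.888 | 79% | 43% |
| 50% | 0.925 | 41% | 53% |
| 75% | 0.963 | 11% | 42% |

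Interaction check at s = 50%: each of the four cells has 187.5 people, with 656.25, 557.8, 656.25 and 656.25 expected episodes. SE² is the sum of reciprocals, 0.00636, so SE = 0.0798, z = 0.1625/0.0798 = 2.037, and power = Φ(2.037 − 1.960) = 53%.

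If both platforms have RR 0.85, pooled power stays at 97%. Adjusting for phone type as a main effect would not reveal a difference like the one in the table; only results by platform would, and as estimates rather than a powered test.

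**The case against.** The strongest reply is that little is at risk. Leaving out stratification factors usually makes standard errors conservative, so it costs some power and creates no false positives. That stands. It is also true that if no iOS version appeared, phone type is constant and there is nothing to adjust for; gender and force still remain. Stratifying survival analyses by up to 8 cells would be sparse, because Hypothesis 1.2 covers only participants with clinically meaningful distress. That too stands and shapes the fix.

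Several stronger readings are tempting, and the documents do not support them:

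- *Pooling platforms biases the comparison of arms.* Randomization within phone strata gives each platform its own concurrent controls, even if iPhone users join later.
- *Two versions of the tool are certainly mixed.* That depends on an iOS release, which the documents do not report. The platform difference is described for Cogito and not for MyCAP.
- *The trial claims to cover every Sailor.* Aim 2 reads "Evaluate the acceptability and feasibility of the Cogito Companion among military personnel (Sailors", and the SAP speaks of a cohort. The phone restriction is disclosed. What is missing is a statement of which platforms the results describe.
- *The feasibility figure should be scaled down for excluded iPhone owners.* Aim 2.2 already lists accrual and technical challenges, feasibility is defined as ease of implementation, and no iPhone share is given.

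**Conclusion.** The concern holds as a modest gap in the analysis plan. The trial stratifies on three factors and then models none of them, and its covariate rule will practically never select them at the planned 950 randomized unless a factor level holds about 4% or less of the sample. If far fewer were randomized, which the SAP's account of pandemic difficulties makes possible, the bound loosens; but selection would then hang on a chance imbalance, which is no better a basis for the model.

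The consequence is lost precision of unknown size, with no bias between arms. If iPhone users were enrolled, there is also no planned way to see whether the Cogito findings apply to one platform or both. The power losses in the illustration depend wholly on an assumed iPhone share and an assumed null effect on iOS; they show what a pooled result could hide and are not a forecast.

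**What to change.** 1. In the OQ-45 episode model, the OQ-45 mixed model and the parallel Hypothesis 1.3 models, include gender and force as prespecified fixed covariates, and phone type where more than one platform was enrolled, whatever the baseline tests show.
2. For the time-to-event comparisons (Hypothesis 1.2 and revised Hypothesis 1.1), keep the Kaplan-Meier curves and add a named regression model with these factors as covariates rather than up to 8 strata.
3. If iPhone users were enrolled, report revised Hypothesis 1.1 and the Aim 2 results by platform, as descriptive estimates with confidence intervals and not as a powered interaction test, and state which platforms were enrolled. If none were, state that the results describe Android users.

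The cost is SAP wording, a few degrees of freedom and imprecise platform estimates. No sample size changes. The SAP is dated 29 May 2023, so if the models have already been fitted, the adjusted versions should be labelled as added analyses.

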## **C. Study Design and Research Methods**

**Recruitment.** [name] (Naval Captain, Co-Investigator on grant) will work with US Fleet Forces Command to identify units viable for participation. Members of such units may be serving on larger (e.g., Aircraft Carrier, ~5000 Sailors) or smaller (e.g., Destroyers, ~300 Sailors) vessels. Post-unit identification, [name] will work with commanding officers to facilitate recruitment efforts, in terms of identifying vessels/Sailors. Members of this research team may present information to potential participants. This could occur on the participating vessels and/or identified military locations. Potential in-person options to inform potential participants regarding the study may range from recruitment on-board vessels during redeployment (recruitment and enrollment tables on ships) to pier-side post-leave during redeployment procedures/all-hands meetings to approximately 36 months post-redeployment.

To facilitate remote recruitment, information regarding the study may be provided to Sailors via email or text, or flyers posted around ships/bases. Although distribution of such information may occur via military personnel, responses to such information (e.g., interest in enrollment) will only be directed to members of the study team. In terms of remote recruitment, Sailors can express interest in the study by calling the study team or completing a short recruitment survey in REDCap. The survey will collect name, phone number, and best day/time to contact the Sailor regarding next steps.

**Consent.** Once interest has been noted, potential participants will be asked to provide verbal consent either in person, over the phone, or via a secure and approved video connection

platform (e.g., VA Video Connect, Zoom) to: 1) confirm eligibility and complete informed consent and baseline measures on the MyCAP/REDCap (Research Electronic Data Capture) smartphone app and/or web-based service 2) be randomized; 3) download either the Cogito Companion smartphone app (Experimental) or the MyCAP/REDCap smartphone app and/or web-based service (Active Control); and 4) complete baseline measures. Further information regarding MyCAP/REDCap (<https://projectmycap.org/> or <https://redcapinfo.ucdenver.edu/>) is provided below.

[figure not shown]
Sailors will be provided with written and/or electronic consent materials. That is, Sailors will be provided with a written copy and/or an electronic copy(ies) of the consent materials. Consent will be obtained via MyCAP/REDCap. This will be facilitated and observed by the team members. During this process, Sailors will be asked to confirm that they have read consent materials and received a written and/or electronic version of consent materials. During the study visit, members of the research team will also explain monitoring processes, and outreach procedures. Such procedures will be initiated in the event that the study team receives technical or clinical data suggesting that such a contact is warranted (more information to be provided below). Participants will be asked to provide the study team with multiple phone numbers via MyCAP/REDCap or in written format for personal (e.g., spouse, friend) and/or provider contact in case the participant cannot be reached during a clinical monitoring outreach call (see below for clinical monitoring procedures).

Randomization will be stratified by gender, force (Surface versus Aviation), and smartphone type (i.e., Android, iPhone [once the iOS version is released]). Initially, only those with Android platform smartphones will be recruited. Once either application is assigned and/or downloaded, a member of the study team will provide the Sailor with the information to login (e.g., tokens). Participants will be provided with study team contact information, for any technical assistance while using the assigned modality, as well as information regarding monthly reimbursement for cell phone data usage (\$30 per month). They will all be provided with Military/Veterans Crisis Line Contact information, and may be provided with additional resources (e.g., local resources). All payments may be made via a MasterCard debit type card called a "ClinCard" that is provided by Greenphire. Funds are usually available via this card within 24 hours following the scheduled payment date (possible exceptions are weekends or holidays).

**Authorization.** All required elements of informed consent will be provided on MyCAP/REDCap, including information regarding the purpose of the study, what to expect if participating, possible risks and discomforts, who is paying for the study, the voluntary nature of participating, whom to contact with questions, information regarding the privacy of participants' information, and exceptions to confidentiality. We will request a Waiver of Documentation of Consent and a HIPAA Waiver to facilitate conducting this study.

**Study Design.** Randomized Controlled Trial (RCT), with up to 1,418 individuals being allocated to Experimental (Cogito Companion) or Active Control (MyCAP) based on stratified randomization tables. Randomization will be stratified by gender, force (Surface, Aviation), and smartphone model (Android, I-Phone [once the iOS version is released]), as Cogito algorithms differ based on smartphone platforms. Data is also being collected (feasibility/acceptability) to inform future implementation.

**Study Procedures.** Upon confirming interest in participating in the study, a member of the research team will obtain verbal informed consent and confirm eligibility. Electronic consent will be provided via MyCAP/REDCap. Baseline measures will be administered via MyCAP/REDCap. Military personnel will then be randomized to the Cogito Companion group (Experimental) or the Active Control (MyCAP) group.

Biweekly (every other week) post-consent, study measures will be pushed to participants via the mobile apps (Cogito Companion, MyCAP). Post-completion of measures at the end of the study period (Follow-up Survey), participants will be provided with a link (MyCAP/REDCap). See Figure 1 for an outline of study procedures, and Table 1 for proposed measures and administration schedule.

